The co-primary efficacy endpoints were the change from week 4 to 6 on the MWT and the ESS. A key secondary endpoint was the percentage of patients reported as worse on the PGI-C and CGI-C, in which they were assessed on a 7-point scale from 1 (very much improved) to 7 (very much worse). Of the 402 patients who were screened, 174 patients were enrolled in the Titration Phase and received at least 1 dose of solriamfetol, and were included in the safety population. Seventeen of the 174 patients (10%) discontinued in the Titration Phase, 9 of 157 patients (6%) discontinued in the Stable-Dose Phase, and an additional 21 patients (14%) did not meet the improvement criteria for randomization. In the Stable-Dose Phase there were 14.6%, 31.8%, and 53.5% of patients in the solriamfetol 75, 150, and 300 mg groups, respectively. The safety population that was randomized to double-blind withdrawal included 62 patients randomized to solriamfetol and 62 patients randomized to placebo. In the Double-Blind Withdrawal Phase there were 7.3%, 21.0%, and 21.8% of patients in the solriamfetol 75 mg, 150 mg, and 300 mg groups, respectively. Two patients discontinued in the Double-Blind Phase; thus, the mITT population consisted of 122 patients (placebo [n=62] and solriamfetol [n=60]).

Baseline values for the MWT and ESS in the mITT population were similar for those in the safety population. After 4 weeks of solriamfetol treatment, MWT sleep latencies increased from approximately 12-13 minutes to approximately 30 minutes and ESS scores decreased from approximately 15-16 to approximately 6 in the mITT population. During the Double-Blind Withdrawal Phase (from week 4 to week 6), patients who had improved on solriamfetol, and who continued to receive solriamfetol, remained improved on the MWT and ESS, whereas patients who were switched to placebo worsened on both measures. From week 4 to week 6 (Double-Blind Withdrawal Period), the mean MWT sleep latency went from 31.7 minutes to 29.7 minutes and the mean ESS score remained at 6.4 at both time points in the solriamfetol group (n=60), while in the placebo group (n=62) the mean MWT sleep latency values went from 29.0 minutes to 17.6 minutes and the mean ESS score went from 5.9 to 10.8.

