Secondary hypotheses include that solriamfetol treatment at maximal patient specific dosing will result in improvements in patient-reported excessive daytime sleepiness and sleep quality (e.g. ESS and PSQI), neurocognitive function (see below for neurocognitive battery), fatigue and mood (e.g. Brief Fatigue Inventory, Cancer Fatigue Scale, Beck Depression Inventory), and quality of life (FACT-Brain).

3. Exploratory Hypotheses

Improvements in objective measures of sleep (e.g. actigraphy, sleep diary) will be similar to those reported in prior studies (e.g. obstructive sleep apnea, narcolepsy). We hypothesize that improvements in sleep, neurocognition, fatigue, mood, and quality of life may vary by clinical factors such as corticosteroid use, antiepileptic use, and tumor grade by World Health Organization (WHO) classification.

3 Objectives

1. Primary Objective(s)

1. To estimate the safety of solriamfetol at 75 mg daily, 150 mg daily, 300 mg daily as assessed by NCI CTC Adverse Events (v5.0) in patients with primary gliomas compared to prior studies⁴⁵⁻⁴⁷

2. Secondary Objective(s)

1. To estimate the effect of solriamfetol on sleep by Epworth Sleepiness Scores (ESS) scores in patients with primary gliomas and compare the effect to previously published scores in patients with OSA
2. To estimate the effect of solriamfetol on sleep quality by Pittsburgh Sleep Quality Index scores
3. To estimate the effect of solriamfetol on neurocognitive function based on a disease-specific neurocognitive battery (see neurocognitive battery below)
4. To estimate the effect of solriamfetol on patient-reported fatigue (Brief Fatigue Inventory, Cancer Fatigue Scale) & mood (Beck's Depression Inventory)
5. To estimate the effect of solriamfetol on patient-reported QOL (FACT-Br)
6. To estimate the effect of solriamfetol on objective sleep-wake times by actigraphy and sleep diary (pre- vs post-treatment)

3. Exploratory Objective(s)

1. To explore a biologic gradient effect of increasing doses of solriamfetol on actigraphy
2. To explore differences in clinical activity of solriamfetol by corticosteroid use, antiepileptic use, and tumor grade

4 Patient Selection

Inclusion and exclusion criteria represent standard criteria for other sleep studies in this population (e.g. inclusion criteria) and standard exclusions for prior studies of this agent (e.g. exclusion criteria).^{8,39,40}

1. Inclusion Criteria

1. WHO Grade 2-4 infiltrating glioma by histologic confirmation

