Storage Requirements: solriamfetol tablets are to be stored at room-temperature conditions, 15°C to 30°C (59°F to 86°F).

Stability: Studies are ongoing to monitor the stability of solriamfetol tablets.

12 Data Management

Informed consent document	EPIC
Protocol registration form	OnCore
Adverse Events Log (Appendix E)	OnCore
Patient Drug Diary (Appendix F)	
Fixed Dose Patient Drug Diary (Appendix G)	
Epworth Sleepiness Scale (Appendix H)	
Pittsburgh Sleep Quality Index (Appendix I)	
Brief Fatigue Inventory (Appendix J)	
Cancer Fatigue Scale (Appendix K)	
Beck's Depression Inventory (Appendix L)	
Neurocognitive Battery Form (Appendix M)	
FACT-Br (Appendix N)	
Concurrent Medication (Appendix O)	OnCore
Off-Study Form (Appendix P)	OnCore
MR Imaging Record (Appendix Q)	
Sleep Diary and Actigraphy Record (Appendix R)	
Glioma History (Appendix S)	

13 Statistical Considerations

This is a single-arm, open label, non-randomized safety study in patients with stable glioma disease. The primary outcome is safety of oral solriamfetol as doses of 75 mg daily, 150 mg daily and 300 mg daily. Secondary outcomes include ESS score, PSQI score, a composite neurocognitive battery score, FSS score, BDI score, and FACT-Br score.

1. Analysis of Primary Objective

For the primary outcome, NCI Common Terminology Criteria for Adverse Events (CTCAE) version 5.0 will be used for scoring toxicity and adverse events.

The severity and frequency of toxicity and adverse events for each dose of solriamfetol will be tabulated using descriptive statistics. The proportions of subjects who experienced grade 3 or above toxicities will be estimated, along with 95% confidence intervals by each type of toxicity.

To compare the safety of solriamfetol at 75 mg daily, 150 mg daily, 300 mg daily, chi-squared statistics will be used. If there are some cells with expected value <5 , Fisher's exact test will be used for the comparison.

2. Analysis of Secondary Objective

For the secondary outcomes, descriptive statistics will be performed for each of the outcome measures. Changes in pre- and post-treatment scores will be assessed and compared using the pair-t tests if the changes follow a normal distribution and using the Wilcoxon signed rank tests if the changes do not follow a normal distribution. For the comparison between the change in ESS score in the study patients and the published change score in patients with obstructive sleep apnea, we will use the one sample t-test for this comparison.

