3. Analysis of Exploratory Objective

13.3.1 To explore the dose response effect of solriamfetol on actigraphy, linear regression models will be used where the dosage will be treated as an ordinal variable.

Transformation of actigraphy will be performed to satisfy the normality assumption if needed.

13.3.2 The analysis will be the same as that specified in 13.1.

4. Power and Sample Size

We plan to recruit around 36 participants.

In the prior phase 2a and phase 2b studies in patients with narcolepsy which had similar sample sizes, no patients in the phase 2a and three patients in the phase 2b study required discontinuation of study medication, though two of these discontinuations were not attributed to the study drug.^{46,47} In the prior phase 3 study, 9 patients (9%) including one in the 75 mg arm, 3 in the 150 mg arm, and 5 in the 300 mg arm required discontinuation due to treatment related AEs.⁴⁵ In the current study, 36 patients will receive 75 mg daily dosing. We conservatively estimate that at least 33 patients will escalate to 150 mg daily, and at least 30 patients will escalate to receive 300 mg daily. These estimates are felt to be overly conservative based on data from these prior studies in patients narcolepsy.

From prior studies, the most common adverse event proportions range from 10% to 20%. Assuming 10% and 20% of adverse event proportion, the detectable proportions for the combined dosage are 24% and 36%, respectively, in order to reach 80% power at a significance level of 0.1 (given the pilot nature of this study) and a two-sided test. These detectable proportions are reasonable. If we observe an adverse event proportion in the patients with primary gliomas that is higher than 36%, then the adverse event proportion is significantly higher than the other study populations. In practice, if an adverse event proportion is higher than 50%, then the safety/tolerability of solriamfetol needs to be questioned. We should have enough power for this primary analysis. Note that this study allows us to determine safety profiles for the 3 doses of solriamfetol. It is primarily for descriptive purpose and to generate data on safety and estimation of effect size for the design of a subsequent randomized study powered to determine drug activity. The results generated from this study will be beneficial for the future research study.

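### The 80% adverse-event power in Section 13.4 is for the pooled doses only, while the primary analysis is by dose; at the stated two-sided 0.10 level, exact power is 66-69% at n=36 and 54-60% at the planned 300 mg minimum of 30

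*Combined protocol and SAP*

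**What the plan says.** Objective 3.1 is dose-specific: "To estimate the safety of solriamfetol at 75 mg daily, 150 mg daily, 300 mg daily as assessed by NCI CTC Adverse Events (v5.0", with comparison to prior studies. Hypothesis 2.1 likewise concerns the side-effect profile at each of the three doses, and serious events at 300 mg relative to the lower doses.

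Section 13.1 follows that structure: "The severity and frequency of toxicity and adverse events for each dose of solriamfetol will be tabulated using descriptive statistics". It adds 95% confidence intervals for grade 3 or higher toxicities by type, and a chi-squared or Fisher test between the three doses.

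Section 13.4 sets the numbers: "We plan to recruit around 36 participants"; "In the current study, 36 patients will receive 75 mg daily dosing"; and "at least 33 patients will escalate to 150 mg daily, and at least 30 patients will escalate to receive 300 mg daily". Its only adverse-event power statement is that "the detectable proportions for the combined dosage are 24% and 36%, respectively, in order to reach 80% power", at a two-sided 0.10 level against 10% and 20%. It then concludes that power for the primary analysis is sufficient, and also describes the study as mainly descriptive. No power or precision figure is given for a single dose or for the between-dose test.

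**The concern.** The power statement and the analysis plan concern different quantities. Section 13.4 powers one proportion over all doses against a fixed published rate. Section 13.1 tabulates by dose and tests doses against each other, with no pooled proportion compared with 10% or 20%. The conclusion in 13.4 is nevertheless applied to the primary analysis without limitation.

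The practical risk lies at 300 mg, the top dose and the default for the six-week continuation phase. If the 300 mg rate is not significantly above published rates, or not significantly above the 75 mg rate, a reader who trusts the 80% figure may take that as support for the hypothesis of a similar profile. The by-dose data cannot bear that weight, and they are meant to inform the design of a later randomised study.

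**Working it through.** **Inputs, all from 13.4:** reference rates p0 = 10% and 20%; alternatives p1 = 24% and 36%; alpha 0.10, two-sided; n = 36, at least 33 and at least 30 at 75, 150 and 300 mg. The sentence on the combined dosage gives no n; 36 is inferred from the planned enrolment.

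**Method.** One-sample exact binomial test. Take the smallest c with P(X ≥ c | n, p0) ≤ t, where t = 0.05 for a two-sided 0.10 test and t = 0.10 for a one-sided one. Power is P(X ≥ c | n, p1). The detectable rate is the smallest p1 with power of at least 80%.

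**Step 1: reproduce the printed pair at n=36.**

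| Method | 24% vs 10% | 36% vs 20% |
|---|---|---|
| Exact, two-sided 0.10 | 66.1% | 68.9% |
| Normal approximation, null variance in the critical value | 79.1% | 73.5% |
| Same, continuity-corrected | 73.1% | 67.6% |
| Arcsine | 73.8% | 69.6% |
| Exact, one-sided 0.10 | 79.5% | 80.2% |

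Only the last row matches both pairs. If the combined dosage instead meant 36+33+30 = 99 patient-dose exposures, power would be about 97-98%, so that reading does not explain the figures either.

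**Step 2: the stated two-sided test at each planned n (t = 0.05).**

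| n | p0 | c | Tail under p0 | Power | Detectable rate |
|---|---|---|---|---|---|
| 36 | 10% | 8 | 0.0235 | 66.1% | 27.2% |
| 36 | 20% | 12 | 0.0424 | 68.9% | 38.9% |
| 33 | 10% | 7 | 0.0417 | 71.0% | 26.3% |
| 33 | 20% | 12 | 0.0216 | 54.8% | 42.2% |
| 30 | 10% | 7 | 0.0258 | 60.4% | 28.7% |
| 30 | 20% | 11 | 0.0256 | 53.8% | 42.7% |

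Over every n from 30 to 36 the ranges are 60-74% and 54-69%; 80% is never reached.

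**Step 3: the one-sided test that matches the printed rates (t = 0.10), at n=30.** c = 6 gives 76.0% (detectable 25.1%) and c = 10 gives 68.4% (detectable 39.3%).

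**Step 4: split the shortfall at n=30 under the two-sided test.**
- 24% vs 10%: 80 − 60.4 = 19.6 points, of which 80 − 66.1 = 13.9 are already present at n=36.
- 36% vs 20%: 80 − 53.8 = 26.2 points, of which 80 − 68.9 = 11.1 are already present at n=36.

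**Step 5: the by-dose test that 13.1 names.** Take 75 mg (n=36) against 300 mg (n=30), treated as independent groups at two-sided 0.10. Power = Φ[(d − 1.645·SE0)/SE1], where d is the difference, SE0 uses the pooled rate and SE1 the separate rates.
- 10% vs 24%: (0.14 − 1.645×0.0915)/0.0926 gives 45.5%; Fisher's exact test gives 39.1%.
- 20% vs 36%: (0.16 − 1.645×0.1101)/0.1101 gives 42.4%; Fisher's exact test gives 36.5%.

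**The case against.** **The study is mainly descriptive, and the figures are labelled as pooled.** Both are true, and no rule in the plan treats non-significance as reassurance; the 36% and 50% marks only flag an excess. This lowers the stakes. But the same paragraph speaks of rates significantly above those of other populations and declares the primary analysis adequately powered, so the statement should be right.

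**Section 13.1 may already pool.** The grade 3 or higher proportions carry no stated dose split, so they could be read as pooled. They concern a different event set from the common adverse events behind the 10-20% rates, and no test against those rates is attached.

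**The 54% is partly a discreteness effect.** This stands. For 36% vs 20%, exact two-sided power is 63.6% at n=29, 53.8% at n=30 and 64.0% at n=32. The loss from 36 to 30 should not be read too finely: by the normal approximation it is about 5-6 points (79.1% to 73.9%, and 73.5% to 67.5%).

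**Two stronger readings are tempting and not supported.** First, a reader might blame the smaller 300 mg group for the whole fall from 80% to 54-60%. Step 4 shows that much of it is the mismatch between the stated two-sided test and a one-sided calculation.

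Second, a reader might infer that 300 mg will have 30 patients or fewer, because in the OSA titration trial "In the Stable-Dose Phase there were 14.6%, 31.8%, and 53.5% of patients in the solriamfetol 75, 150, and 300 mg groups, respectively". Section 13.4 plans a minimum of 30, not a maximum. The OSA share counts patients settled on 300 mg after titration up or down every 3 days, not everyone who ever took it. Here escalation is scheduled unless a dose-limiting toxicity occurs. Losing patients only at that trial's titration dropout would leave (174 − 17)/174 × 36 = 32.5. The phase 2a and 2b narcolepsy trials cited in 13.4 also escalated on a schedule: all 33 patients completed phase 2a, and 3 of 44 (6.8%) on solriamfetol stopped for adverse events in phase 2b. The planning figure of at least 30 can stay.

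**Conclusion.** The concern holds in a limited form and should be corrected. The 80% claim is attached to a pooled comparison that 13.1 does not specify, and it does not apply to the by-dose primary analysis. Under the stated two-sided 0.10 level it is not met even for the pooled 36 patients, where exact detectable rates are about 27% and 39% rather than 24% and 36%. At the 300 mg minimum of 30 they are about 29% and 43%. If a one-sided test was meant, the pooled figures stand, and n=30 gives detectable rates of about 25% and 39%.

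This rests on n=36 for the pooled figures, published rates treated as fixed, and, at 300 mg, a one-sample comparison that follows objective 3.1 but is not written into 13.1. The 37-46% for the between-dose test assumes independent groups; the same patients pass through the doses, so it is indicative only.

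**What to change.** 1. In 13.1, add the pooled adverse-event proportion (any dose, each patient counted once, N=36), compared with the 10% and 20% reference rates, as the analysis to which the 13.4 power refers.
2. In 13.4, limit the power sentence to that analysis. Either state that the test is one-sided at 0.10, or keep it two-sided and replace 24% and 36% with about 27% and 39%. Print detectable rates or confidence-interval precision by dose at n=36, 33 and 30. As an illustration, for an observed 20% the approximate 95% half-width is 1.96×√(0.2×0.8/n): 13.1, 13.6 and 14.3 points.
3. State that dose-specific results are estimates with confidence intervals, and that a non-significant 300 mg or between-dose comparison is not evidence of a similar profile.

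The cost is wording in 13.1 and 13.4 and one extra table, with no added patients or procedures. The downside is that the stated power becomes less favourable.

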4. Preliminary Data on Sleep-Wake Disturbance in Gliomas and Rationale for Solriamfetol

At the American Academy of Neurology Annual Meeting, we recently presented the results of a pilot cross-sectional study evaluating the prevalence, risk factors, associated symptoms, and quality of life impact of self-reported sleep-wake disturbances in a cohort of patients with primary gliomas (Figure 2).

Figure 2: Study design from the prior cross-sectional study of sleep disorders in brain tumors patients

[figure not shown]

Figure 3: Prevalence of patient-reported excessive daytime sleepiness by Epworth Sleepiness Scale (ESS) scores

A prospective cohort of 50 brain tumor patients was recruited to complete a one-time survey-based assessment of self-reported sleep disturbance using the Epworth Sleepiness Scale (ESS), Pittsburgh Sleep Quality Index (PSQI), a previously validated sleep hygiene and sleep habits questionnaire, as well as clinical and treatment

[figure not shown]
characteristics, and quality of life (e.g. EQ-5D). In this study, excessive daytime sleepiness (EDS, ESS \geq 10) was reported in 46% of brain tumor patients (Figure 3). Patient-reported ESS was generally correlated with caregiver observed ESS for the patient ($r=0.56$, $p=0.005$), though important differences were present at the extremes of patient ESS. Abnormally low ESS (ESS<5) was observed in 16% of patients, meaning that a normal ESS score was only observed in 36% of the cohort. Self-reported excessive daytime sleepiness (ESS \geq 10) was significantly more common in patients who had ever undergone chemotherapy (42% vs 22%, $p<0.008$) but not radiation therapy ($p=0.30$) or by tumor grade ($p=0.25$). Fifty-two percent of patients on active corticosteroids had ESS \geq 10 compared to only 28% of those not taking corticosteroids ($p=0.17$). Chemotherapy treatment was associated with nighttime awakenings ($p=0.04$) while corticosteroid use was associated with lower daytime energy ($p=0.04$). EDS was also associated with poorer health-related QOL including reduced mobility ($p<0.03$) and impaired daily activities ($p<0.02$). These preliminary data support that:

1. Sleep-wake disturbances in the form of patient-reported excessive daytime sleepiness are common in brain tumor patients
2. That patient ESS can be used to evaluate self-reported sleep dysfunction given the correlation with caregiver observation, and

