ESS score is the most important secondary outcome in this study. We also calculate the power to test whether the pre-post change is different from 0 and test whether the change is different from the pre-post change in the prior studies which recorded the pre-post changes for patients at 75 mg, 150 mg, and 300 mg. At an alpha of 0.10, a two-sided test, and cohort sample size of 36 patients, the study will have 80% power to detect the mean difference of 1.01 point ($=0.42$ standard deviation (SD)) in ESS score from the study sample. The mean differences are reasonable. We should have enough power for our analysis.

Prior studies of solriamfetol in patients with narcolepsy have demonstrated improvement in ESS scores at Week 8 of -3.4 (75 mg daily), -5.2 (150 mg daily), -6.4 (300 mg daily), and -2.1 (placebo) with baseline ESS ranging from 16.9-17.3. In patients with OSA, Week 8 improvements were -6.3 (75 mg daily), -6.9 (150 mg daily), -7.7 (300 mg daily), and -3.8 (placebo) in patients with baseline ESS ranging from 14.8 to 15.6. In our prior study mean ESS score for patients with primary brain tumors who would be eligible for the proposed study (i.e. ESS \geq 10) was 14.8 (SD: 2.4). For the current study, we will use the data from the prior OSA study as a comparator given that baseline ESS scores were similar to what we anticipate in the to-be-enrolled cohort. Based on this, the study hypothesizes that treatment with solriamfetol at 75 mg, 150 mg, or 300 mg will achieve at least a 6.3 point difference (75 mg daily) and up to 7.7 point difference (300 mg daily) in ESS scores at Week 10 (baseline vs V3). This will be compared to a null difference of 3.8 (placebo arm in OSA study). This mean change in ESS scores is clinically meaningful as has been reported.⁵³ In order to detect the differences between the mean change ESS score from the proposed study to the mean change of 3.8 in the placebo arm in OSA study, the detectable mean change needs to be greater than 5.4 in the study sample in order to reach 80% power. We hypothesize that the mean change in this study sample ranges from 6.3 to 7.7, which is higher than 5.4. We should have sufficient power to detect the difference between the mean change ESS score in our study sample and that in the placebo arm in the OSA study.

5. Estimated Accrual Rate

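### Section 13.4's two detectable ESS changes (1.01 against 0, and 5.4 against 3.8) cannot both come from the planned one-sample test, and no SD of change is stated

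*Combined protocol and SAP*

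**What the plan says.** Section 13.4 calls ESS the most important secondary outcome and announces two calculations in one sentence: the "power to test whether the pre-post change is different from 0 and test whether the change is different from the pre-post change" seen in earlier studies. One set of inputs follows, "At an alpha of 0.10, a two-sided test, and cohort sample size of 36 patients", with one result: "80% power to detect the mean difference of 1.01 point ($=0.42$ standard deviation (SD)) in ESS score from the study sample".

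The next paragraph sets a null change of 3.8, the Week 8 placebo change in the sleep apnea study, and says "the detectable mean change needs to be greater than 5.4 in the study sample in order to reach 80% power". It concludes: "We hypothesize that the mean change in this study sample ranges from 6.3 to 7.7, which is higher than 5.4". SD, alpha and n are not restated beside 5.4.

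Section 13.2 plans a paired t-test for pre-post change (Wilcoxon signed rank if the changes are not normal) and a one-sample t-test for the comparison with the published sleep apnea change.

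The only ESS SD in Section 13.4 is 2.4, around a mean of 14.8, for patients in the group's earlier study with a score of 10 or more. Section 1.4 describes that study as one in which patients were recruited to "complete a one-time survey-based assessment of self-reported sleep disturbance".

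**The concern.** A paired t-test is a one-sample t-test on the change scores. For a given SD of change, n, alpha and power it detects the same distance from the null, whether the null is 0 or 3.8. Section 13.4 gives distances of 1.01 and 1.60 for the same outcome in the same 36 patients.

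The SD is a second problem. The figure of 2.4 that reproduces 1.01 matches the spread of single scores in a one-time survey, and such a survey cannot supply an SD of change.

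Section 13.4 draws a conclusion of adequate power from each figure, yet the two imply different SDs of change. A reader cannot tell which variability was planned for, or how much power the study has for a small change against 0.

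**Working it through.** **Inputs.** From Section 13.4: n = 36, two-sided alpha 0.10, 80% power, null values 0 and 3.8, stated detectable changes 1.01 and 5.4, hypothesized change 6.3 to 7.7, SD of single scores 2.4. From Section 13.2: one-sample (paired) t-test.

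**Method.** Power comes from the noncentral t distribution with 35 degrees of freedom and noncentrality (difference/SD) × √36. Solving for 80% power gives a detectable difference of 0.4227 SD.

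**First figure.** 0.4227 × 2.4 = 1.014, so 1.01 reproduces with SD 2.4. Working back, 1.01/0.4227 = 2.39.

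**Second figure.** With the same inputs, 3.8 + 1.014 = 4.81, not 5.4. With SD 2.4, a true change of 5.4 has 98.9% power against 3.8, not 80%.

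**Size of the gap.** (5.4 − 3.8)/1.01 = 1.60/1.01 = 1.58. Rounding of the stated figures allows 1.55/1.015 = 1.53 to 1.65/1.005 = 1.64, so rounding does not explain it.

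**SD that 5.4 requires.** 1.60/0.4227 = 3.79 (3.67 to 3.90 for 5.35 to 5.45). With that SD the detectable change against 0 is 1.60, and power for 1.01 is about 47%.

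**Is 2.4 an SD of change?** With equal variances at both visits, SD of change = 2.4 × √(2(1 − r)), where r is the pre-post correlation. This is 2.40 at r = 0.5 and 3.39 at r = 0. The protocol states no correlation.

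**Can other inputs give 5.4?**

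| Calculation | Result against 3.8 |
|---|---|
| One-sample, n = 36, alpha 0.05, SD 2.4 | 4.95 |
| One-sample, n = 30, alpha 0.10, SD 2.4 | 4.92 |
| One-sample, n = 36, alpha 0.05, SD 3.39 | 5.43 |
| One-sample, n = 30, alpha 0.10, SD 3.39 | 5.38 |
| Two-sample, 36 vs 36, alpha 0.05, SD 2.4 | 5.41 |
| Two-sample, 36 vs 114, alpha 0.10, SD 3.39 | 5.42 |

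Changing only alpha, or only n to 30, is not enough. With SD 2.4 and alpha 0.10, 5.4 would need n of about 15 to 16. The last four rows come close, but each uses an SD that the protocol does not state or a test and alpha that differ from those it does state.

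**Effect of the SD of change** (SDs of 3 to 6 are an assumption; n = 36, two-sided alpha 0.10):

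| SD of change | Detectable against 0 | Detectable against 3.8 | Power for 1.01 against 0 | Power for 6.3 against 3.8 |
|---|---|---|---|---|
| 3 | 1.27 | 5.07 | 63% | 99.9% |
| 4 | 1.69 | 5.49 | 44% | 98% |
| 5 | 2.11 | 5.91 | 33% | 90% |
| 6 | 2.54 | 6.34 | 26% | 79% |

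The largest SD with 80% power for 6.3 against 3.8 is 2.5/0.4227 = 5.9 with 36 patients. If only 30 had end-of-treatment data (an illustration), it would be 2.5/0.4649 = 5.4.

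**The case against.** The strongest reply is that the two figures need not share inputs. The opening sentence refers to changes at the three active doses in earlier studies. The comparison with the placebo change of 3.8 comes only in the next paragraph, where alpha, n and SD are not repeated. The closing words of that paragraph, which set the study sample against the placebo arm, would fit a two-sample calculation, and several such combinations give about 5.4. On that reading the fault is undocumented inputs rather than wrong arithmetic, and if 2.4 is the right SD, 5.4 errs on the cautious side.

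Part of this stands. The inputs behind 5.4 cannot be identified, and an unstated calculation may lie behind it. But the detectable margin is the same whether the comparator is an active or a placebo change, and the ESS change in these patients has one SD. A two-sample calculation would not match the test in Section 13.2.

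It is also fair that no conclusion changes: 6.3 exceeds both 4.81 and 5.4, ESS is secondary, and Section 13.4 describes the study as mainly descriptive. A later randomized trial would draw on the effect size and SD observed here, so the planning SD matters little for that purpose. These points limit the consequence, but the two figures remain incompatible under the planned test.

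**Conclusion.** The concern holds and should be fixed. Under the one-sample test of Section 13.2, with the alpha and n given in Section 13.4, 1.01 and 5.4 imply SDs of change of 2.4 and about 3.8, and at most one can be right. That 2.4 was taken from the single-score survey SD is an inference from the matching value; the protocol does not say which SD it used.

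The consequence is limited. Adequate power for 6.3 against 3.8 does not depend on settling the discrepancy unless the SD of change is above about 5.9. The claim that is exposed is 80% power for 1.01 against 0, which fails if the SD of change is appreciably above 2.4.

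**What to change.** Restate the ESS part of Section 13.4 with one SD of change and its source, and with one test, alpha and n for both figures, using the one-sample/paired t-test of Section 13.2. If no SD of change is available, show an openly assumed range. Possible wording:

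> Power is for the two-sided one-sample t-test on ESS change from baseline to V3 (alpha 0.10, 36 patients). No estimate of the SD of change in glioma was available for planning. For assumed SDs of 3, 4, 5 and 6, the change detectable with 80% power is 1.27, 1.69, 2.11 and 2.54 against 0, and 5.07, 5.49, 5.91 and 6.34 against 3.8. Power for 6.3 against 3.8 is at least 80% for an SD up to 5.9.

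The sponsor should confirm the second sentence of this wording before using it.

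If 2.4 is kept as the SD of change, justify it as such and change 5.4 to 4.81. If 5.4 is kept under this test, state an SD of change of 3.8 with a source, and change 1.01 to 1.60. If a two-sample calculation was intended, say so with its inputs and reconcile it with Section 13.2.

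The cost is recalculated wording in one section, with no extra patients and, under the first three options, no change to the planned test. The stated detectable change against 0 becomes less favourable if the SD of change exceeds 2.4.
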